#### 7.2.1.2 Intensity of an Adverse Event

All AEs will be assessed by the investigator using the following guidelines to quantify intensity:

- Mild: Events that do not interfere with daily activities and require no medical intervention.
- Moderate: Events that cause some interference with daily activities and may require simple medical interventions.
- Severe: Events that prevent usual daily activities and require medical intervention.
- Life-threatening: Any adverse drug experience that places the subject, in the view of the investigator, at immediate risk of death from the reaction as it occurred, i.e., it does not include a reaction that had it occurred in a more severe form, might have caused death.
- Fatal: Any AE that causes the death of the subject. Except for sudden and unexpected death, death is not an AE, but rather the event that caused the subject to die is the AE.

Changes in the intensity of an AE should be documented to allow an assessment of the duration of the event at each level of intensity to be performed. AEs characterized as intermittent require documentation of onset and duration of each episode.

#### 7.2.1.3 Relationship to Study Agent

The investigator's assessment of an AE's relationship to study agent is part of the documentation process, but it is not a factor in determining what is or is not reported as an AE in the study. If there is any doubt as to whether a clinical observation is an AE, the event should be reported. All AEs must have their relationship to study agent assessed using the following terms: associated or not associated. "Associated with the use of the study agent" means that there is a reasonable possibility that the experience may have been caused by the study agent [61]. In a clinical trial the study agent must always be suspect. To help in assessing the relationship to study agent, the following guidelines are used.

- **Associated** The event is temporally related to the administration of the study agent and no other etiology explains the event.
- **Not Associated** The event is temporally independent of study agent and/or the event appears to be explained by another etiology.

Events assessed as being associated with study agent will be further classified as possibly, probably or definitely related to study agent.

Events assessed as being not associated with study agent will be further classified as probably not or definitely not related to study agent.

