### 5.5 Dose-limiting Toxicity

- Every AE recorded in this study must be assessed by the investigator to determine whether or not it meets the definition of a dose-limiting toxicity (DLT).
- A DLT is defined as any toxicity determined by the investigator to be related to the study agent and deemed serious or sufficiently severe to preclude dose escalation.
- For the purpose of this study, any grade 4 or 5 event (per the Common Terminology Criteria for Adverse Events (CTCAE) v4.0 criteria) that is assessed as possibly, probably or definitely related to the study drug will be considered to be a DLT.

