#### 7.2.1.4 Relationship to Intravitreal Injection Procedure

All AEs will also be assessed for their relationship to the intravitreal injection procedure used to administer the study agent, using the same categories as described in Section 7.2.1.3.

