Summaries of TEAEs by maximum intensity will be presented for ocular AEs and non-ocular AEs separately. The number of subjects with any TEAEs (along with percentages) will be tabulated by SOC and PT within each SOC by treatment group. To count the number of subjects with any TEAEs, if a subject has multiple TEAEs coded to the same PT within the same SOC, the subject will be counted once under the maximum severity.

The relationship of each AE to the study drug/intravitreal injection procedure should be determined by the Investigator using these explanations:

- Associated The event is temporally related to the administration of the study agent/ intravitreal Injection procedure and no other etiology explains the event.
- Not Associated The event is temporally independent of study agent intravitreal Injection procedure and/or the event appears to be explained by another etiology.

Events assessed as being associated with the study agent or associated with the intravitreal injection procedure will be further classified as possibly, probably or definitely related to study agent or injection procedure.

Events assessed as being not associated with study agent or injection procedure will be further classified as probably not or definitely not related to study agent or injection procedure.

All AEs will be presented in a by-subject listing. AEs leading to study treatment discontinuation, all serious AEs, and DLTs will also be presented in separate listings.

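### Protocol 7.2.1.3 defines an associated event as a reasonable possibility, but its working bullets, the only part SAP 14.1 repeats, require that no other etiology explains the event, so agent-related events and DLTs can be under-counted

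*Protocol*

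**What the plan says.** Protocol 7.2.1.3 first gives a definition. Association with the agent "means that there is a reasonable possibility that the experience may have been caused by the study agent", and the section adds: "In a clinical trial the study agent must always be suspect".

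It then offers two bullets as guidelines to help the rating.

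- The first sets the condition for *associated*, in these words: "The event is temporally related to the administration of the study agent and no other etiology explains the event".
- The second sets the condition for the opposite rating, *not associated*, and reads: "The event is temporally independent of study agent and/or the event appears to be explained by another etiology".

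The grades possibly, probably and definitely related are subdivisions of *associated*. *Not associated* splits into probably not and definitely not related.

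Protocol 7.2.1.4 has every AE rated for the injection as well, "using the same categories as described in Section 7.2.1.3". SAP 14.1 reproduces the bullets for agent and injection, including the condition that "no other etiology explains the event", but omits the reasonable-possibility sentence.

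Under Protocol 5.5, a grade 4 or 5 event "assessed as possibly, probably or definitely related to the study drug will be considered to be a DLT". The general limb of the DLT definition also requires that the investigator judge the toxicity related to the agent.

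**The concern.** The definition asks whether the agent could have caused the event. The bullets ask whether anything else explains it. These questions give different answers whenever an event has a second credible cause, and in this trial ocular events often will.

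Every dose is an intravitreal injection, so agent and procedure share the same timing. Under the bullets, an ocular event that the agent may have caused can be rated *not associated* with it because the injection or the underlying retinoschisis appears to explain it. Such an event cannot be graded even *possibly related*, although that grade is the natural one for an event with competing causes.

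The rating decides whether a severe event is a DLT, whether a serious unexpected event is reported on the expedited timeline, how long an ongoing non-serious event is followed, and whether it enters the agent-related tables. Two investigators could classify the same event differently and both cite the section.

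**Working it through.** **Step 1. Compare the standards.**

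| Event | Definition | Bullets |
|---|---|---|
| Temporally related, no other explanation | Associated | Associated |
| Temporally related, agent a reasonable possibility, another etiology appears to explain it | Associated | Not associated |
| Temporally independent of the agent, no reasonable possibility | Not associated | Not associated |

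The standards part in the second row, where the bullets remove events from *associated*. They add none, provided that a temporally related event with no other explanation always counts as a reasonable possibility. The sentence that keeps the agent under suspicion supports that proviso. The count under the bullets is therefore at most the count under the definition. The *and/or* in the second bullet matters: a rival explanation is enough even when the timing fits, and it need only appear to explain the event.

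**Step 2. Check that rival explanations exist.** Protocol 1.3.1 lists inflammation, retinal breaks and retinal detachment as risks of the agent, and inflammation, retinal holes, tears and detachments as risks of any intravitreal injection. In the macaque study (Protocol 1.1.4.3.2), vehicle injection alone produced aqueous cells from trace to 4+ at one week. Protocol 1.1.1 and 1.2.1 name retinal detachment and vitreous hemorrhage as complications of the disease.

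**Step 3. Trace where the rating is used.**

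| Depends on the rating | Does not depend on it |
|---|---|
| DLT classification (Protocol 5.5, SAP 14.1) | Recording of all AEs (Protocol 7.2.1.3, 7.3.1) |
| Automatic enrollment pause after a DLT (5.6, 7.4.1) | Grade 3 or 4 primary safety parameter (7.1.1) |
| Expedited reporting of serious unexpected events (7.3.3) | SAP primary variables (SAP 3.1) |
| Follow-up of ongoing non-serious AEs after Month 12 (7.3.6) | SAE reporting to the sponsor within 24 hours (7.3.2) |
| Agent- and injection-related TEAE tables (SAP 14.1) | DSMC review of safety data between groups (5.6, 7.4.2, 10.7.5) |

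**Step 4. The plan's DLT figures.** Protocol 10.5 gives 95% upper limits for the DLT rate when none is seen. The two-sided exact limit for 0 of n is 1 − 0.025^(1/n):

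- n = 9: 1 − 0.025^(1/9) = 33.63%, as stated.
- n = 27: 1 − 0.025^(1/27) = 12.77%, as stated.

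These limits bound the rate of *counted* DLTs. Let s be the share of true agent-related DLTs that are rated associated. The counted rate is then s times the true rate, so the limit on the true rate is the stated limit divided by s. The documents give no value for s; the range below is an assumption, applied to the unrounded limits.

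| s (assumed) | n = 9 | n = 27 |
|---|---|---|
| 1.00 | 33.63% | 12.77% |
| 0.75 | 44.84% | 17.03% |
| 0.50 | 67.25% | 25.54% |
| 0.25 | 100% (capped) | 51.08% |

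The table shows how the stated limits depend on complete attribution. It does not estimate s.

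**The case against.** The best defense is that the section has an order of authority. The definition says what association means, and the bullets are only guidelines to help apply it. An investigator who keeps to the definition loses no events. This stands: under-counting is a possible result of following the bullets, not a demonstrated fact. It helps less with the SAP, which repeats the bullets without the definition.

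A reader might infer that agent and injection exclude each other, so that an event drops out of both ratings. The documents do not support that as the expected result. It would require judging that the injection explains the event when rating the agent, and that the agent explains it when rating the injection; those judgements conflict. Nothing in 7.2.1.4 makes the two ratings mutually exclusive. A shift from agent to injection is the more natural outcome, and a shifted event still appears in the injection-related tables (SAP Tables 14.3.7, 14.3.8 and 14.3.11) and in the listing of all AEs.

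A reader might also infer that these counts decide dose escalation. They do not. Protocol 5.6, 7.4.2 and 10.7.5 rest progression on DSMC review of safety data for all enrolled participants, with no DLT-count threshold. The absence of DLTs appears in Protocol 1.2.2 only as rationale. Under 7.3.3, SAEs rated not associated still reach the DSMC in summary at each between-cohort review.

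Finally, the change log for protocol version 8.0 refers to a completed 12-month analysis, so new wording cannot alter decisions already taken and could mix two standards in one dataset. That is a reason for disclosure, not for leaving the contradiction in place.

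**Conclusion.** Wrong as written. Protocol 7.2.1.3 contradicts itself on what makes an event associated with the agent, and SAP 14.1 carries forward only the narrower standard. Relative to the protocol's own definition, the bullets can lower the number of agent-related events and DLTs and cannot raise it. This direction rests on the proviso in Step 1. The size depends on how investigators applied the section and cannot be determined from the documents. The limits of 33.63% and 12.77% describe the true agent-related DLT rate only if every such event is rated associated.

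The consequences are confined to the left-hand column in Step 3. The documents do not support a claim that safety events are hidden from the DSMC or that the primary safety result is biased.

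**What to change.** 1. In Protocol 7.2.1.3 and SAP 14.1, reword *associated* as a reasonable possibility that the agent (or, for the second rating, the injection procedure) caused the event, and *not associated* as no such reasonable possibility.
2. State in both documents that one event may be associated with both agent and procedure, and that a plausible role for one does not by itself exclude the other.
3. Add a row for TEAEs related to agent and/or procedure to the overall summary (SAP Table 14.3.1). Both ratings are already collected for every AE under Protocol 7.3.1, so this needs no new data.
4. For events already classified, report which standard was applied.

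The drafting cost is small: wording in two places and one table row. There are two downsides. More events will count as related, and earlier and later classifications may differ, which must be disclosed if past events are not reassessed. No dose or clinical management rule changes.

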#### 7.2.1.4 Relationship to Intravitreal Injection Procedure

All AEs will also be assessed for their relationship to the intravitreal injection procedure used to administer the study agent, using the same categories as described in Section 7.2.1.3.

#### 7.2.1.5 Serious Adverse Event (SAE)

An SAE is any untoward medical occurrence that at any dose:

- Results in death,
- Is life-threatening. Any AE that places the subject, in the view of the investigator, at immediate risk of death from the reaction as it occurred. This **does not** include a reaction that, had it occurred in a more serious form, might have caused death.
- Requires in-patient hospitalization or prolongation of existing hospitalization. This does
  not include hospitalization for elective or pre-planned surgery, *unless* prolonged
  hospitalization occurs due to complications from the surgical procedure,
- Results in persistent or significant disability or incapacity,
- Results in a congenital anomaly/birth defect,
- Is an event that required intervention to prevent permanent impairment or damage,
- Any other important medical events that do not result in death, are not life-threatening, or do not require hospitalization may be considered SAEs when, based upon appropriate medical judgment, the event may jeopardize the participant and might require medical or surgical intervention to prevent one of the previously described outcomes. Examples of such medical events include allergic bronchospasm requiring invasive treatment in an emergency room or at home, blood dyscrasias or convulsions that do not result in inpatient hospitalization, or the development of drug dependency or drug abuse.

# 7.3 Reporting Procedures

#### 7.3.1 Adverse Events

All AEs should be captured on the appropriate electronic case report form (eCRF). Information to be collected includes event description, date of onset, intensity, relationship to study agent, relationship to the intravitreal injection procedure used to administer the study agent, action taken, date of resolution or stabilization of the event, seriousness, and outcome (resolved, ongoing or death caused by the AE). All AEs occurring while on study must be documented and treated appropriately regardless of relationship. All AEs will be followed until resolution, until the condition stabilizes, until the event is otherwise explained, or the subject is lost to follow-up.

Any medical condition that is present at the time that the subject is screened should be considered as a pre-existing condition and not reported as an AE; however, if it deteriorates at any time during the study it should be recorded as an AE.

#### 7.3.2 Serious Adverse Events

All AEs that meet the criteria for an SAE as defined in Section 7.2.1.5 must be reviewed and evaluated by a study physician and captured on the appropriate SAE eCRF. The SAE eCRF must be complete within the following timelines:

- Every AE with onset during or after study agent administration that meets the protocol defined criterion for a designation of serious or a DLT must be reported to the Sponsor by recording on the subject's AE eCRF within 24 hours of the Investigator or study staff's first knowledge of the event.
- Entry of SAE or DLT information in the eCRF will trigger an e-mail to the Sponsor to take appropriate action in response to the information.
- In any instance in which the database cannot be accessed, a paper SAE form must be completed and faxed to the Sponsor (at AGTC [contact]), followed by a phone call within 24 hours of the Investigator or study staff's first knowledge of the event.

A separate set of SAE eCRF pages should be used for each SAE. However, if at the time of initial reporting, multiple SAEs are present that are temporally and/or clinically related, they may be reported on the same SAE eCRF page.

DLT reporting will follow the same timeline as SAE reporting.

The investigator should attempt to establish a diagnosis of the event based on signs, symptoms, and/or other clinical information. In such cases, the diagnosis should be documented as the AE and/or SAE and not the individual signs/symptoms. New or updated information should be recorded on the originally completed SAE eCRF pages.

If a subject dies during participation in the study, a copy of any post-mortem findings, including histopathology, should be provided when available as an attachment to an updated SAE eCRF page.

Other supporting documentation of the event may be requested and should be provided as soon as possible.

Questions about SAE reporting can be referred to [name] at AGTC [contact], [name].

### 7.3.3 Regulatory Reporting

Following notification from the investigator, the sponsor will report events that are both serious and unexpected and that are associated with study agent to the US Food and Drug Administration (FDA) within the required timelines as specified in 21 CFR 312.32, *i.e.*, fatal and life-threatening events within 7 calendar days (by telephone or fax) and all other SAEs in writing within 15 calendar days. These SAEs will also be reported to the Institutional Review Board (IRB) at each site, the NIH Office of Biotechnology Activities, and other site-specific committees according to regulatory requirements. SAEs designated as not associated with study product will be reported in a summary format to the DSMC during each between-cohort review and to the FDA at least annually.

### 7.3.4 Reporting of Pregnancy

Not applicable - females will not participate in this study.

# 7.3.5 Procedures to be Followed in the Event of Abnormal Laboratory Test Values

Any clinically significant abnormal laboratory test result will be recorded as an AE, and if it meets the criteria defined in Section 7.2.1.5 it will be reported as an SAE.

### 7.3.6 Follow-up of Adverse Events

All SAEs and DLTs must be followed and treated as appropriate until resolution. An SAE or DLT is considered resolved when the subject returns to their baseline condition, or when the event has stabilized, as in the case of an event with sequelae, in which case the event will be noted as "resolved with sequelae".

If an SAE or DLT is still ongoing at the visit 12 months after study drug administration, follow-up of the event will be done at each follow-up visit until the end of the study.

If an SAE or DLT is still ongoing when the subject is lost to follow-up, the study site staff needs to complete the following steps to ensure the proper follow up the SAE or DLT:

- Complete and document two separate attempts to contact the subject and/or their emergency contact by telephone at an appropriate clinically indicated interval for followup of the event;
- If attempts to contact the subject are unsuccessful, send a certified letter to the subject's last known address requesting that the subject contact the study site.

Non-serious AEs that are assessed as "related" to the study agent will be followed and treated as appropriate until the end of the study, including evaluation at long-term follow-up visits if the event is ongoing at the visit 12 months after the study drug administration.

Non-serious AEs that are evaluated as "not related" to the study agent, and that are ongoing at the visit 12 months after the study drug administration, will be characterized as "ongoing" at that visit, and further follow up will not be required.

The investigator is responsible for ensuring that follow-up includes any supplemental investigations that may be indicated to elucidate as completely as practical the nature and/or causality of the AE or SAE. This may include additional laboratory tests or investigations, histopathological examinations, or consultation with other health care professionals.

# 7.4 Data and Safety Monitoring Plan

#### 7.4.1 Temporary Suspension of Study Agent Administration

Within groups 1A, 1B, 2, 2A, and 3, enrollment of participants will be staggered by at least 2 weeks to allow adequate time for review of safety information by the investigators and sponsor. Within group 4, enrollment of the first 3 pediatric participants in each group will be staggered by at least 2 weeks to allow adequate time for review of safety information by the investigators and sponsor. If any participant within any study group develops a dose-limiting toxicity (as defined in Section 5.5), enrollment of additional participants will not proceed until review by the DSMC.

#### 7.4.2 Criteria for Enrollment in Subsequent Groups

Enrollment will begin with Group 1A and will proceed to subsequent groups only after review of safety data by the DSMC. After review of safety data from Group 1A, participants will be enrolled in Groups 1B and 2 concurrently. After review of safety data from Groups 1A, 1B and 2, participants will be enrolled in Group 3. After review of safety data from Groups 1A, 1B, 2 and 3, participants  $\geq$ 18 years of age will be enrolled in Group 4 As ocular inflammation has been seen in the first 12 subjects enrolled in the study and pediatric participants might be more prone to inflammation, pediatric participants (age 6-17) in this study will first be treated at the middle dose (Group 2A) prior to the enrollment at Group 4.

Each safety review will be conducted based on data for all enrolled participants accrued up to and including the visit 2 weeks after administration of rAAV2tYF-CB-hRS1 to the last participant enrolled in Group 1A (for the first review), 2 weeks after administration of rAAV2tYF-CB-hRS1 to the last participant enrolled in Groups 1B and 2 (for the second review) ,2 weeks after administration of rAAV2tYF-CB-hRS1 to the last participant enrolled in Group 3 (for the third review), or 2 weeks after administration of rAAV2tYF-CB-hRS1 to the last participant enrolled in Group 3 (for the third review), or 2 weeks after administration of rAAV2tYF-CB-hRS1 to the last participant enrolled in Group 2A (for the fourth review).

The length of time between dosing participants may be extended if the investigators, sponsor, DSMC or FDA believes that additional time is needed to ensure safety of the participants.

